##### **9.3.2.2.1.3 Preterm Labor**

Preterm labor will be based on HCP reported diagnosis. It is often as regular contractions of the uterus resulting in changes in the cervix that start before 37 weeks of pregnancy. Any interventions or treatments provided to the patient as a result of preterm labor will be collected.

##### **9.3.2.2.1.4 Gestational Diabetes**

Gestational diabetes will be based on HCP reported diagnosis. It is often characterized by the development of carbohydrate intolerance with first onset or first recognition during pregnancy; a record of an oral glucose tolerance test during pregnancy will also be accepted for data collection, where available ([ACOG, 2018](#)).

#### **9.3.2.2.1.5 Placenta Previa**

Physician-diagnosed placenta previa: when the baby's placenta fully or partially covers the mother's cervix.

#### **9.3.2.2.2 Pregnancy Outcomes**

##### **9.3.2.2.2.1 Elective or Therapeutic Pregnancy Terminations**

Elective or therapeutic pregnancy terminations are defined as any induced or voluntary fetal loss during pregnancy. If available, data from pathologic examination of the abortus or fetus will be evaluated by the adjudication committee (see [Section 9.8.4](#)) for structural and chromosomal defects. The reason for elective or therapeutic termination will be collected. Elective versus therapeutic terminations will be summarized separately.

##### **9.3.2.2.2.2 Spontaneous Abortions**

A spontaneous abortion is defined as loss of a fetus due to natural causes at < 20 weeks of gestation. If available, information from gross or pathologic examination of the abortus or fetus will be evaluated by the adjudication committee (see [Section 9.8.4](#)) for structural and chromosomal defects.

##### **9.3.2.2.2.3 Fetal Death or Stillbirth**

Fetal death or stillbirth refers to the death of a fetus prior to birth at or after 20 weeks of gestation. In the event of a stillbirth or fetal death, full pathology details will be requested and examined for structural or chromosomal defects. The final classification between fetal death/stillbirth and spontaneous abortion will be based on gestational age.

##### **9.3.2.2.2.4 Live Birth**

A live birth refers to a complete expulsion or extraction from its mother of a surviving neonate.

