#### 9.2.1.1.2 European Surveillance of Congenital Anomalies (EUROCAT)

EUROCAT is a European network of population-based registries for the epidemiologic surveillance of congenital anomalies (EUROCAT, 2017). Started in 1979, the registry includes over 1.7 million births surveyed annually in Europe from 43 registries in 23 countries. Approximately 29% of the European birth population is covered by this network. These population-based registries facilitate the early warning of new teratogenic exposures, evaluate the effectiveness of primary prevention measures, and assess the impact of developments in prenatal screening.

Using 13 registries from the EUROCAT network from 01 January 1998 through 31 December 2011, Groen et al. reported an overall prevalence of congenital anomaly of 27.3 per 1000 births (range, 19.1–39.3 per 1000 births) (Groen et al, 2017). Of the 84,387 pregnancies with a known outcome (99.4%), 2.33% pregnancies were stillbirths, the proportion of early neonatal mortality (within 7 days of birth) was 2.37% and the proportion of late neonatal mortality (between 7 days to 27 days of life) was 0.84%.

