##### **9.3.2.2.2.5 Preterm Birth**

A live birth will be classified as preterm prior to 37 weeks of gestation ([www.cdc.gov](http://www.cdc.gov)). Preterm birth will be categorized as early preterm (< 34 weeks), late preterm (34 weeks to 36 weeks), and early term (37 weeks to 38 weeks).

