#### 9.7.2.4 Analysis of the Primary and Secondary Endpoints

The prevalence of major and minor congenital malformations will be calculated using MACDP convention. Major malformations will be analyzed separately from minor malformations, with the primary analysis including only adjudicated major congenital malformations. The total prevalence will be calculated by dividing the number of adjudicated cases of each event (observed in live births, fetal deaths, elective or therapeutic terminations, and at any gestational age) by the total number of pregnancies (excluding spontaneous terminations and ectopic or molar pregnancies). The prevalence at birth will be calculated as number of cases observed in live births and stillbirths divided by the total number of births (stillbirths + live births). Data analysis for major congenital malformations will be based on first trimester exposure to erenumab-aooe.

The prevalence of pregnancy complications, including preeclampsia, pregnancy-induced hypertension, gestational diabetes, placenta previa, and preterm labor, will be summarized by dividing the number of each event by the total number of pregnant women.

The prevalence of spontaneous abortions will be calculated by dividing the number of fetal losses occurring before 20 weeks gestation by the total number of pregnancies.

The prevalence of elective and therapeutic abortion will be estimated similarly as separate outcomes.

Prevalence of preterm birth will be calculated by dividing the number of cases by the total number of births (stillbirths + live births). The prevalence of small-for-gestational-age will be calculated by dividing the number of cases by the total number of live births.

For growth and developmental delays, the prevalence will be calculated as the number of cases divided by the total number of live births.

Prevalence of primary and secondary outcome measures will be presented with 95% CIs for binomial proportion. The analyses summarized in this section will be performed on the erenumab-aooe exposed cohort and the internal comparator cohort consisting of pregnant women with migraine who were not exposed to erenumab-aooe; Characteristics can be matched or stratified in relation to the exposed cohort to control for important covariates such as maternal age (see [Section 9.7.2.5.1](#)).

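### The live-birth definition requires a surviving neonate, so its wording can leave a neonatal death without an outcome class; separately, preterm live births are divided by live births plus stillbirths

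*Protocol*

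**What the plan says.** Three outcome definitions in Protocol Section 9.3.2.2.2 and the formulas in Section 9.7.2.4 bear on this.

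- Live birth (9.3.2.2.2.4): "A live birth refers to a complete expulsion or extraction from its mother of a surviving neonate". There is no signs-of-life criterion and no time to which survival refers.
- Stillbirth (9.3.2.2.2.3): "Fetal death or stillbirth refers to the death of a fetus prior to birth at or after 20 weeks of gestation".
- Preterm birth (9.3.2.2.2.5): "A live birth will be classified as preterm prior to 37 weeks of gestation". The Abstract also restricts preterm birth to live births.
- Total malformation prevalence (9.7.2.4): the numerator is adjudicated cases "observed in live births, fetal deaths, elective or therapeutic terminations, and at any gestational age". They are divided "by the total number of pregnancies (excluding spontaneous terminations and ectopic or molar pregnancies").
- Malformation prevalence at birth (9.7.2.4): "The prevalence at birth will be calculated as number of cases observed in live births and stillbirths divided by the total number of births (stillbirths" plus live births).
- Preterm prevalence (9.7.2.4): "Prevalence of preterm birth will be calculated by dividing the number of cases by the total number of births (stillbirths + live births").
- Size for gestational age (9.3.2.2.3.2 and 9.7.2.4): live births only.

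Neonatal death is not among the listed outcomes. Section 9.1 mentions infant death only as a reason for follow-up to stop. The birth form (Appendix F, Table 3) offers four pregnancy outcomes: spontaneous abortion, termination, live birth and stillbirth.

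**The concern.** Stillbirth needs death before delivery, and live birth, taken at its word, needs survival. A baby delivered alive who then dies as a neonate meets neither test. Every formula above is built on those classes, so the word *surviving* decides who is counted.

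The timing of data collection makes this more than a matter of style. Birth information is collected about 4 weeks after the estimated date of delivery. By then most early neonatal deaths have occurred, so the person coding the outcome will often know whether the infant survived. Two coders could classify the same infant differently.

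The infants at issue are likely to include those with lethal malformations or extreme prematurity. If they went uncounted, the error would run towards missing harm.

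The preterm formula has its own mismatch. A stillbirth enters the denominator but can never be a case.

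**Working it through.** **1. The plan's own figure.** Inputs from Section 9.5: 3% in the comparator, risk ratio 2.0 (so 6% in the exposed), 80% power, alpha 0.05, 1:1. The sides of the test are not stated; two-sided reproduces the figure. With pooled variance and no continuity correction:

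n = [1.960 × √(2 × 0.045 × 0.955) + 0.842 × √(0.03 × 0.97 + 0.06 × 0.94)]² / 0.03² ≈ 749 per group, with power 80.0%.

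749 / (0.85 × 0.62) = 1421.3, stated as 1421. Both figures reproduce and neither is disputed.

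**2. Where a neonatal death would go on the literal reading.**

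| Analysis (Section 9.7.2.4) | Numerator | Denominator |
|---|---|---|
| Malformation prevalence at birth | leaves | leaves |
| Total malformation prevalence | leaves | stays (pregnancies) |
| Preterm birth | leaves | leaves |
| Size for gestational age | leaves | leaves |

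**3. How many malformation cases.** Section 9.2.1.1.2 reports for affected pregnancies in the European registries that "the proportion of early neonatal mortality (within 7 days of birth) was 2.37"%, with a further 0.84% for late neonatal mortality. The sum is 3.21%.

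- Comparator: 749 × 0.03 = 22.5 cases. × 0.0237 = 0.53; × 0.0321 = 0.72.
- Exposed at risk ratio 2: 749 × 0.06 = 44.9 cases. × 0.0237 = 1.07; × 0.0321 = 1.44.

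**4. Effect if the loss is equal in both cohorts.** In total prevalence, 3.00% × (1 − 0.0321) = 2.90% and 6.00% × (1 − 0.0321) = 5.81%. The risk ratio stays 2.00 and power at 749 per group is 78.7%. Removing the infants from the denominator as well, as in prevalence at birth, gives 2.91% against 5.82%, a risk ratio of 2.00 and power of 78.7%.

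**5. Effect if the loss differs.** The comparator loss is held at 3.21%. The exposed losses below are assumptions; the protocol gives no such figures.

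| Assumed share of exposed cases lost | Observed risk ratio | Power |
|---|---|---|
| 5% | 0.0570 / 0.02904 = 1.96 | 76% |
| 10% | 0.0540 / 0.02904 = 1.86 | 68% |
| 20% | 0.0480 / 0.02904 = 1.65 | 48% |

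**6. Preterm denominator.** Let s be stillbirths as a share of all births. Dividing by live births plus stillbirths instead of live births multiplies the proportion by (1 − s). Section 9.2.1.1.1 gives s = 8.0 and 7.6 per 1,000. The factor is 0.9920 or 0.9924, an understatement of 0.80% or 0.76% relative. If stillbirth were twice as frequent in one cohort (an assumption), the preterm risk ratio would change by the factor (1 − 0.016) / (1 − 0.008) = 0.992.

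**The case against.** The best defence is that *surviving* belongs to the act of delivery. Set beside a stillbirth definition that turns on death before birth, it can simply mean alive at expulsion, and then there is no gap. Other sections fit that reading. Section 9.4.2 reserves infant follow-up contacts for live births, while Section 9.1 lists infant death as a reason for follow-up to stop, so an infant who dies during follow-up is already being treated as a live birth. Section 9.7.1.2 puts adjudicated malformations reported up to 1 year of age into the primary analysis without a survival condition.

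This stands, and it limits the point. A reader might infer that the protocol removes all live-born infants who die from its malformation, preterm and size analyses. The documents do not support that. No section states such an exclusion. The definition speaks of a neonate, so a death later in infancy is not touched. In total malformation prevalence the pregnancy remains in the denominator.

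Nor can it be shown that the registry's rates would fail to match the main external source. Section 9.2.1.1.1 says only that its prevalence is per 1,000 live births, not how early deaths are treated.

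The 3.21% is also borrowed. It describes European affected pregnancies, whereas Section 9.7.1.2 excludes detected aneuploid and genetic disorders from the primary analysis.

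The defence does not reach the preterm formula, which is inconsistent however *surviving* is read. It is small and applies equally to both cohorts.

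**Conclusion.** The point holds as a defect of wording plus one inconsistent formula. Severity is minor.

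Taken literally, the live-birth and stillbirth definitions leave a neonatal death unclassified, and several analyses depend on that classification. On the protocol's mortality figures the exposure is about 0.5 to 0.7 of 22.5 comparator cases and 1.1 to 1.4 of 45 exposed cases per 749 live births. At 3.21% equal loss, power moves from 80.0% to 78.7% and the risk ratio does not move. A biased risk ratio requires lethal cases to differ between cohorts, and the figures given for that are illustrations on assumed loss shares. All of this assumes the literal reading is applied and the cited mortality carries over.

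The preterm mismatch needs no such assumption about reading. It understates the proportion by under 1% relative at the stillbirth rates that the protocol cites.

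**What to change.** - Section 9.3.2.2.2.4: define live birth as complete expulsion or extraction of a neonate showing any sign of life, whether or not it later dies.
- Section 9.7.2.4: divide preterm live births by live births, which matches the preterm definition in Section 9.3.2.2.2.5.

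Reporting neonatal death separately among live births would be a useful addition but is optional; the correction does not depend on it.

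The cost is two sentences. No new data are needed, because pregnancy outcome, its date and infant serious adverse events with their outcome are already collected (Section 9.2.8; Appendix F, Tables 3 and 4). The sample size is unchanged.

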##### **9.3.2.2.2.5 Preterm Birth**

A live birth will be classified as preterm prior to 37 weeks of gestation ([www.cdc.gov](http://www.cdc.gov)). Preterm birth will be categorized as early preterm (< 34 weeks), late preterm (34 weeks to 36 weeks), and early term (37 weeks to 38 weeks).

#### **9.3.2.2.3 Infant Outcomes**

##### **9.3.2.2.3.1 Minor Congenital Malformations**

Congenital malformations will be classified according to the MACDP classification system (see [Section 9.2.1.1.1](#)) and minor congenital malformations are part of the secondary objectives for this study. All potential minor congenital malformations will be evaluated by at least 3 qualified, independent teratologists using all available medical

records (see [Section 9.8.4](#)). The classification of potential minor congenital malformations will be based upon the teratologists' adjudication, who will be blinded to patient exposure status. Adjudicated minor congenital malformations will not be included in the analysis of the primary objective.

#### **9.3.2.2.3.2 Size for Gestational Age**

All live births will be classified as small, appropriate, or large for gestational age using the Centers for Disease Control and Prevention (CDC) definition ([www.cdc.gov](http://www.cdc.gov)) of birth weight below the 10th percentile, between the 10th and 90th, and above the 90th percentile for age, respectively.

#### **9.3.2.2.3.3 Low Birth Weight**

An infant with low birth weight will be classified as weighing under 2500 g ([www.cdc.gov](http://www.cdc.gov)). Low birth weight can be subclassified into very low birth weight (< 1500 g) and moderate low birth weight (1500 g to 2499 g).

#### **9.3.2.2.3.4 Postnatal Growth and Development**

Domains of developmental milestones (ie, social/emotional, language/communication, neurocognitive, movement/physical development milestones) by age will be defined by guidelines provided by the CDC ([CDC 2019](#)). As recommended by the CDC, the World Health Organization Growth Charts (suitable for use in the U.S. from birth to 24 months) will be applied for this study, where infant growth measurements will be used to estimate gender-specific weight-for-length, head circumference-for-age, length-for-age, and weight-for-age percentiles. Developmental milestones will be collected as part of routine clinical practice with pediatrician-determined results of infant status (ie, below, above, or at age appropriate achievement) in each of the domains listed above. "Ages and Stages" or similar standardized assessments may be collected for this study if performed as part of routine clinical care – no additional information will be mandated for collection as part of this study.

### **9.3.3 Covariate Assessment**

#### **9.3.3.1 Baseline Covariates**

- Patient demographics and characteristics:
  - Age of patient (mother) at the time of enrollment
  - Education level (Doctoral or professional degree, Master's degree, Bachelor's degree, Associate degree, Postsecondary nondegree award, some college, no degree, High school diploma or equivalent, No formal educational credential)
  - Race (American Indian or Alaska Native, Asian, Black or African American, Hawaiian or Other Pacific Islander, White, Other/Unspecified)

- Ethnicity (Hispanic or Latino and Not Hispanic or Latino)
- Height (cm or in)
- Weight (kg or lbs.); pre-pregnancy and current weight
- Body mass index (BMI) (derived from height and current weight)
- Lifestyle risk factors
  - Smoking (current, former, never)
  - Caffeine consumption (Y/N)
  - Alcohol use (Y/N; if Y, drinks per week)
  - Illicit drug use (Y/N)
- Current pregnancy information (calendar provided to help recall)
  - Date of LMP
  - Gestational age at the time of enrollment visit
  - EDD
  - Date and results of any prenatal tests
  - Pregnancy complications (ie, physician reported preeclampsia, pregnancy-induced hypertension, preterm labor, gestational diabetes, placenta previa)
  - Pregnancy history
    - Parity: number of pregnancies carried to a viable gestational age (> 20 weeks)
    - Gravidity: number of pregnancies
    - Previous preterm births (for definition, see [Section 9.3.2.2.2](#))
    - Previous spontaneous abortions (for definition, see [Section 9.3.2.2.2](#))
    - Previous elective or therapeutic terminations (for definition, see [Section 9.3.2.2.2](#))
    - Reason for any elective or therapeutic termination,
    - History of congenital malformations
    - Other (specify)
- Surgical and medical history or significant maternal medical conditions other than migraine (eg, diabetes, high blood pressure)
- Migraine history, including type(s) of migraine (chronic, episodic), presence of aura, age at migraine onset, number and duration of migraines and migraine days in the past month (patient-reported), average monthly migraine days prior to pregnancy, number of prior preventive migraine treatment failures (pre-pregnancy), days of acute migraine treatments each month (pre-pregnancy and by trimester), impact of pregnancy on the intensity of headache
  - If diagnosed with chronic migraine, age at chronic migraine onset

- Family reproductive history, including:
  - Multiple births
  - Pregnancy complications (ie, preeclampsia, pregnancy-induced hypertension, preterm labor, gestational diabetes, placenta previa)
  - Congenital malformations
  - Spontaneous abortions
  - Preterm births
  - Chromosomal anomalies
  - Evidence of developmental delays
- Erenumab-aooe treatment (including start and stop dates, dose, dosing frequency, reason for discontinuation [if applicable])
- Current and prior medication use starting from 3 months prior to LMP (including all prescription and any other OTC migraine treatment(s), folic acid and other vitamins, herbal remedies or supplements, vaccinations, or other medications used to treat chronic conditions or comorbidities); including start and stop dates (if applicable)
- Patient AEs and SAEs (including event, start date, ongoing or end date, seriousness, severity, relationship to erenumab-aooe, outcome, action taken)

#### **9.3.3.2 Covariates During Follow-up**

Covariates to be collected during pregnancy, at delivery, during infant follow-up and at early termination of study participation (if applicable) are described in [Section 9.2.8](#).

#### **9.3.4 Validity and Reliability**

Data will be collected from the patient's HCP or directly from the patient and entered into the eCRF by trained CC staff (see [Section 9.4](#)). Standard definitions for the classification of pregnancy outcomes have been used and proper citations have been provided, where applicable. Some outcomes, such as pregnancy complications, will rely on the report of a diagnosis (eg, hypertension) and not individual measurements (eg, systolic and diastolic blood pressure values). Reliability of the data is subject to what is reported by the HCP and/or patient, and methods to ensure the quality of the data to the extent possible is provided in [Section 9.6.1](#). Published literature can be used for comparison of the distribution and/or frequencies of key covariates.

The primary outcome of major congenital malformations and the secondary outcome of minor congenital malformations will be defined using the standard classifications provided by MACDP, with an independent review by a committee of teratologists who will be blinded to the patient's exposure status (see [Section 9.8.4](#)).

## **9.4 Data Sources**

### **9.4.1 Collection of Data on the Electronic Case Report Form**

Patients' data obtained via questionnaires administered to patients or their HCPs will be recorded on eCRFs by the CC. The degree of detail and completeness of data collected is dependent on local clinical practice.

### **9.4.2 Data Collected During the Observation Period**

The CC is responsible for patient enrollment (ie, determining eligibility and obtaining informed consent and permission for medical form release) and obtaining all patient and HCP contacts. After a patient provides consent, the CC will obtain demographic and contact information in addition to baseline information at the time of enrollment. All patient and HCP contact information will be confidential and will remain at the CC. Infant HCP contact information will be obtained at the delivery follow-up (estimated within 4 weeks of delivery date). The CC will then contact the patient each trimester to update contact information and ascertain the occurrence of pregnancy outcomes or other events (see [Section 9.3](#) for list of variables). Below is a list of the expected contact points for data collection with patients and HCPs:

#### **Expected contacts with patient:**

- Enrollment
- End of Trimester 1 (approximately 14 gestational weeks)
- Mid-Trimester 2 (approximately 21 gestational weeks)
- Mid-Trimester 3 (approximately 34 gestational weeks)
- EDD plus 4 weeks
- Birth plus 12 weeks, 26 weeks, and 52 weeks (live births only)

#### **Expected contacts with the patient's HCP (eg, PCP, neurologist [indication specialist], OB, nurse midwife):**

- Enrollment
- Mid-Trimester 2 (approximately 21 gestational weeks)
- EDD plus 4 weeks

#### **Expected contacts with the infant's HCP (eg, pediatrician) (live births only):**

- EDD plus 4 weeks
- Birth plus 12 weeks
- Birth plus 26 weeks
- Birth plus 52 weeks

After a patient is enrolled, there will be at least 3 attempts made to contact the patient and/or the HCP via phone, email, fax, and mail, as appropriate, approximately 10 business days apart. If data is obtained after a follow-up interval is passed, the CC will accept and enter the data and continue follow-up of the patient. If an HCP is not responsive at the time points described above, the patient will be asked to provide the information contained on the HCP questionnaires administered by the CC for eCRF entry. If the HCP then responds to contact, their information will supersede the patient-reported information. At all time points, the type of reporter (patient, PCP, neurologist [indication specialist], OB, nurse midwife or pediatrician) will be recorded.

In the routine care setting, patients are seen regularly by their treating physicians either for treatment or for regular assessment after treatment. Thus, no study-specific visits or evaluations are required by this protocol.

If the patient experiences an adverse pregnancy outcome or has an elective or therapeutic termination or a termination of unknown cause, the HCP and patient will be encouraged to report the outcome to the CC as soon as possible. In the event of an elective or therapeutic termination, spontaneous abortion, fetal death or stillbirth, communications with the patients will cease after pregnancy outcome information has been obtained. Amgen Safety will follow-up on all SAEs, including information about fetal or maternal death, with the patient's HCP.

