### 9.2.8 Study Follow-up

Women will be followed from enrollment through the end of their pregnancy and infants will be followed through 1 year after birth. Specific data to be collected during different periods during the follow-up are detailed below. Safety reporting will be ongoing throughout the duration of the study.

---

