**Infant Follow-up (estimated at 12, 26 and 52 weeks of age)**

- Reporter of information (eg, patient, PCP, OB, neurologist [indication specialist], nurse midwife, infant HCP, other)
- Feeding behavior (including breastfeeding)
- Weight
- Length
- Head circumference
- Postnatal growth and development (ie, social/emotional, language/communication, neurocognitive, movement/physical development milestones)
- Breastfeeding status
- Evidence of any new congenital malformations and growth alterations since last follow-up
- Vaccination information
- Patient and infant AEs and SAEs (including event, start date, ongoing or end date, seriousness, severity, relationship to erenumab-aooe, outcome, action taken)

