#### **9.4.5 Safety Data Collection**

All AEs and SAEs in the erenumab-aooe exposed cohort are required to be recorded in the eCRF during the observation period. HCPs will report AEs and SAEs occurring during pregnancy through the infant's first year of life to the CC, who will enter them in the eCRF. See [Section 11](#) for a full description of safety procedures.

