### **9.7.3 Analysis of Safety Outcomes**

Interim safety reporting will be conducted every year and will be aligned with the periodic benefit-risk evaluation report (PBRER) reporting schedule. All AE verbatim terms will be recorded and coded using the Medical Dictionary for Regulatory Activities version 21.1 or later. All AEs reported will be analyzed by preferred terms on overall and within erenumab-aooe exposed and internal comparator cohorts.

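### Maternal AEs are sought until 52 weeks after a live birth, but no section fixes an end after a pregnancy loss, so the cohort AE tables pool unequal collection periods

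*Protocol*

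**What the plan says.** - Section 9.2.8, opening: "Women will be followed from enrollment through the end of their pregnancy and infants will be followed through 1 year after birth". The same paragraph adds that safety reporting continues for the whole study.
- Section 9.2.8, infant follow-up at 12, 26 and 52 weeks: the items collected include "Patient and infant AEs and SAEs", so mothers are covered as well as infants. Section 9.4.2 restricts the patient contacts at those times to live births.
- Section 9.4.2, after a loss or termination: "communications with the patients will cease after pregnancy outcome information has been obtained". The next sentence adds: "Amgen Safety will follow-up on all SAEs, including information about fetal or maternal death, with the patient's HCP".
- Section 9.4.2, contact lists: the contact at EDD plus 4 weeks, for both the patient and her HCP, is not restricted to live births.
- Section 9.4.5: "HCPs will report AEs and SAEs occurring during pregnancy through the infant's first year of life to the CC". It gives no end point for a pregnancy that produces no infant.
- Section 11.2: safety events are collected to the end of follow-up. Pregnancy loss is not named among the events that end it.
- Appendix F, Table 3 (about 4 weeks after EDD): the form lists spontaneous abortion, termination and stillbirth as outcomes and has patient AE fields.
- Section 9.7.3: "All AEs reported will be analyzed by preferred terms on overall and within erenumab-aooe exposed and internal comparator cohorts".

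**The concern.** A mother's AE collection period depends on how her pregnancy ends. A woman with a live birth is asked about AEs for a further year. A woman with a loss is not asked again once the outcome is recorded, and what her HCP is asked afterwards is not defined. Pregnancy outcome is itself something the registry compares between cohorts. If the cohorts differ in loss rate, or if one enrols earlier and so has more of its losses observed, the maternal AE table compares unequal observation time. The registry answers a regulatory requirement to evaluate maternal as well as fetal and infant outcomes. When collection stops is a protocol matter, because no later analysis can recover events that were never sought.

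**Working it through.** **1. Do the sections agree on when maternal AE collection ends?**

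| Section | Live birth | Loss or termination |
|---|---|---|
| 9.2.8 opening | end of pregnancy; safety reporting ongoing | the same |
| 9.2.8 infant follow-up, with 9.4.2 contacts | 52 weeks after birth | no such contact |
| 9.4.2 text | not addressed | patient contact stops when outcome recorded; SAEs via HCP |
| 9.4.5 | infant's first year | undefined |
| 11.2 | end of follow-up | end of follow-up; loss not named as an end |

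These cannot all be followed after a loss. The patient contact at EDD plus 4 weeks is listed for all outcomes, yet the 9.4.2 text cancels it. The corresponding HCP contact is not cancelled, but neither is it confirmed. Section 9.2.8 times the delivery contact within 4 weeks of delivery, while 9.4.2 times it from EDD. For a loss at week 10 these are about week 14 and about week 44.

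**2. How many women are affected?** Inputs from Section 9.5: 1,421 enrolled, 15% drop-out, 62% live births, 749 live births needed. The protocol's own figure is checked first.

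- 3% against 6%, 80% power, alpha 0.05 (taken as two-sided), pooled variance without continuity correction: 749 per group, as stated.
- 749 / (0.85 × 0.62) = 1,421.3, against 1,421 stated.
- Followed: 1,421 × 0.85 = 1,208. Without a live birth: 1,208 × 0.38 = 459 per cohort.

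**3. How unequal are the periods?** Timings are assumptions; the protocol gives none. Live birth is at week 40, and the outcome is learned at once.

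- Enrolment at week 6, loss at weeks 8 to 19: 2 to 13 weeks of patient-reported AE time. Live birth: 34 + 52 = 86 weeks.
- Enrolment at week 12, loss at weeks 14 to 19: 2 to 7 weeks. Live birth: 28 + 52 = 80 weeks.

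**4. What could this do to crude AE counts?** Assume a constant and equal AE rate in both cohorts, enrolment at week 12, birth at week 39 (27 + 52 = 79 weeks of AE time) and loss at week 16. One cohort has 62% live births, the other 66% or 70%; this difference is assumed.

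*Nothing collected after the loss (4 weeks per loss):*
- 62%: 0.62 × 79 + 0.38 × 4 = 50.5 weeks
- 66%: 0.66 × 79 + 0.34 × 4 = 53.5 weeks; ratio 0.94
- 70%: 0.70 × 79 + 0.30 × 4 = 56.5 weeks; ratio 0.89

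*HCP contact at EDD plus 4 weeks applied after the loss (44 − 12 = 32 weeks per loss):*
- 62%: 0.62 × 79 + 0.38 × 32 = 61.1 weeks
- 66%: 0.66 × 79 + 0.34 × 32 = 63.0 weeks; ratio 0.97
- 70%: 0.70 × 79 + 0.30 × 32 = 64.9 weeks; ratio 0.94

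The cohort with fewer live births would show 6–11% fewer AEs per woman on the first reading and 3–6% fewer on the second. With equal live-birth rates and equal timing the artefact vanishes.

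**5. Is drug still present when patient contact stops?** Section 9.1 gives a 28-day half-life, so the fraction left is 0.5^(days since last dose / 28), and 5 half-lives are 140 days (3.1% left).

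- Last dose week 4, loss week 10: 1.5 half-lives, 35% left.
- Last dose 16 weeks before LMP, loss week 8: 6 half-lives, 1.6% left.
- Last dose week 4, stillbirth week 30: 6.5 half-lives, 1.1% left.

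Spontaneous abortion is defined as before 20 weeks (140 days), so after any dose on or after LMP it falls inside 5 half-lives. That is not so for every loss.

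**The case against.** The strongest reply is that Section 9.4.2 stops communication with the patient, not AE collection. Serious AEs have a stated route through the HCP. The form at about EDD plus 4 weeks already accommodates losses and patient AEs, and Appendix E draws AE collection as a continuous arrow from enrolment. AE frequency is not a primary or secondary objective; the defined maternal outcomes are pregnancy complications. Section 9.7.3 is descriptive, and denominators are commonly left to the SAP.

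Much of this stands. The gap is mainly in non-serious and newly arising events, and the absence of a denominator is not a fault in itself. What remains is that the protocol does not say whether the HCP contact happens after an earlier loss or how far it reaches, while mothers of live-born infants are plainly asked for longer.

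Three stronger readings are tempting and are not supported:

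- **Complications of a loss are systematically missed.** Serious ones are followed with the HCP, and others may reach the existing form.
- **The AE table leans toward safety by a known amount.** That needs a higher loss rate or earlier enrolment in the exposed cohort, and the protocol states neither. Section 9.4.5 requires AE recording specifically in the exposed cohort, and 11.2 refers to events after exposure to the drug. Fuller recording in exposed women would push the other way.
- **AE collection ends while drug is still present.** This fails for many women exposed only before LMP and for late stillbirths after early dosing. It has no meaning for the unexposed cohort. The 16 weeks in Section 9.1 is an eligibility window before LMP, not a safety follow-up period.

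**Conclusion.** The point holds as a defect in the collection rule. Non-serious and newly arising maternal AEs are sought over periods that depend on pregnancy outcome, and four sections disagree or are silent on the end after a loss. On the planning rates in Section 9.5 this touches about 459 women per cohort after drop-out. The effect on the crude cohort comparison is conditional: it requires cohorts that differ in loss rate or in gestational age at enrolment. The 3–11% range above illustrates assumed differences and is not an estimate. The sample size and the primary malformation analysis are untouched. The change is worth making because it is cheap and removes an avoidable distortion from the maternal AE tables.

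**What to change.** 1. Reconcile Sections 9.2.8, 9.4.2, 9.4.5 and 11.2 so that each pregnancy outcome has one stated end of maternal AE and SAE collection.
2. State in Section 9.4.2 that the existing HCP contact at EDD plus 4 weeks also applies after a loss or termination, and that it covers maternal AEs and SAEs since the outcome. No further call to the patient is needed.
3. In Section 9.7.3, tabulate maternal AEs by cohort over the window common to all outcomes (with step 2, enrolment to about EDD plus 4 weeks). Report later AEs in mothers of live-born infants separately.

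The cost is protocol wording and some extra form completion by HCPs after losses. The form and its AE fields already exist, and no contact with bereaved patients is added.
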